### **Objective**

In this study, we investigated the clinical characteristics of patients with acute myocarditis in Korea and sought to find out the treatment results and prognosis of fulminant myocarditis requiring vasopressors or mechanical assist devices.

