### **Design**

Patients diagnosed with acute myocarditis from January 2004 to December 2021 at 6 domestic institutions were investigated for baseline characteristics and clinical course.

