### **Method**

#### 1) Analysis method

- Review medical records and reanalyze previously performed blood tests, electrocardiograms, echo-cardiographic tests, imaging tests, and biopsies.
- Clinical results (in hospital mortality, death from any cause, heart transplantation, permanent left ventricular assist device insertion, hospitalization) and changes in echocardiographic findings of patients treated for myocarditis should be confirmed prior to the clinical trial approval date.

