## **Statistical Analysis Plan (SAP)**

All data for statistical test are analyzed using SPSS and R. All measurements for continuous variables are expressed as mean  $\pm$  standard deviation, and measurements for discrete variables are expressed as percentages. Student's t-test is used for comparative analysis of continuous variables, and  $\chi^2$ -test is used for comparison between two groups for discrete variables. After treatment for myocarditis, recovery of myocardial function and correlation with clinical results were analyzed using paired t test and Kaplan-Meier survival analysis. Predictors of death and factors requiring ECMO treatment were identified through binary logistic regression analysis. Binary logistic regression

analysis requires the occurrence of 10-15 events per independent variable, but in this study, about 30%, or about 270 people, are expected to die, so enough risk factors can be studied. The goodness of fit of the risk prediction model will be tested by C-statistic and Hosmer-Lemeshow tests. In addition, death or re-hospitalization during follow-up will be estimated by the Cox survival analysis method. After checking the fitness of the model by checking Schoenfeld's residual, the hazard of each risk factor is identified. A case of  $P < 0.05$  is considered statistically significant.

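### The plan names no internal validation for its logistic prediction model, so the reported C-statistic and calibration will look better than they are

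*Combined protocol and SAP*

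**What the plan says.** The SAP section plans logistic models for two outcomes: "Predictors of death and factors requiring ECMO treatment were identified through binary logistic regression analysis". It supports the size of these models with a rule of thumb, that such "analysis requires the occurrence of 10-15 events per independent variable", and then reasons that "about 30%, or about 270 people, are expected to die, so enough risk factors can be studied". Performance is covered by a single sentence: "The goodness of fit of the risk prediction model will be tested by C-statistic and Hosmer-Lemeshow tests".

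Nothing else in the SAP bears on the performance of the logistic models. The Schoenfeld residual check belongs to the separate Cox analysis and concerns proportional hazards. The Design section describes one cohort, "Patients diagnosed with acute myocarditis from January 2004 to December 2021 at 6 domestic institutions", with no validation set. The plan gives no list of predictors for the models and no selection method.

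**The concern.** The C-statistic says how well a model ranks patients. It says nothing about whether predicted risks agree with observed risks, so calling it goodness of fit is a mislabel. That is the smaller matter.

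The larger one is where the two checks are made. With one cohort and no validation step, the natural reading is that both are computed in the development data. There, the fitted coefficients have already adapted to chance features of the sample. The C-statistic is then biased upward, and Hosmer-Lemeshow, which compares the model with the data it was fitted to, has little chance of showing that predictions are too extreme for new patients.

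The events-per-variable rule is the plan's only safeguard. It limits overfitting but neither measures nor corrects it. A reader would take the apparent C-statistic and a non-significant Hosmer-Lemeshow test as the model's accuracy and calibration.

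**Working it through.** **1. The plan's own figures.** The SAP expects about 270 deaths at about 30%. It states no cohort size, so 270 cannot be derived independently; it implies 270 / 0.30 = 900 patients. The rule then allows 270 / 15 = 18 to 270 / 10 = 27 parameters. This is a ceiling, not a stated model size. No ECMO count is given. If 10% of 900 were treated (assumed), 90 events would allow 90 / 15 = 6 to 90 / 10 = 9 parameters. At 20% (assumed), 180 events would allow 180 / 15 = 12 to 180 / 10 = 18.

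**2. Quantities.** Optimism = C-statistic in the development data minus C-statistic of the same fitted model in new patients from the same population. Calibration slope = coefficient of the model's linear predictor when it is refitted in new patients; 1 is ideal, and below 1 means predictions are too extreme.

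**3. Assumptions.** The documents give no effect sizes, so these are assumed: N = 900; independent standard-normal predictors; 8 with a real effect (log odds ratio 0.55, 0.35 or 0.20 per SD) and the rest null. The 5- and 6-predictor models omit 3 and 2 of the real ones. There were 300-400 simulated cohorts per scenario (150 with selection), each tested on 20,000 new patients. The Monte Carlo standard error of the optimism is 0.001-0.002. With 8 predictors, the true C-statistic for death is 0.819, 0.734 and 0.642 at the three effect sizes.

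**4. Optimism in the C-statistic, death model (270 events).**

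| Model | 0.55 | 0.35 | 0.20 | Calibration slope, strong to weak |
|---|---|---|---|---|
| 5 pre-specified | 0.006 | 0.009 | 0.014 | 0.97-0.91 |
| 8 pre-specified | 0.009 | 0.012 | 0.019 | 0.95-0.88 |
| 18 (15 events each) | 0.017 | 0.025 | 0.041 | 0.91-0.75 |
| 27 (10 events each) | 0.026 | 0.039 | 0.058 | 0.86-0.65 |
| Backward selection, P<0.05, from 38 | 0.017 | 0.025 | 0.047 | 0.91-0.70 |

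The last row is illustrative. The observational-data and clinical-test lists contain roughly 34-38 items, depending on how they are counted, but the plan does not declare them candidate predictors.

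**5. ECMO model, on the assumed rates.** At 90 events, optimism is 0.012-0.033 with 6 predictors and 0.015-0.043 with 9. At 180 events it is 0.015-0.036 with 12 and 0.022-0.052 with 18.

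**6. Hosmer-Lemeshow.** P was 0.05 or more in 92-98% of models in every scenario, including those with slopes near 0.65.

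**7. Does bootstrap correction work?** Share recovered = (apparent - corrected) / (apparent - new patients). Each row is a separate run of 60 cohorts, with 60 resamples each (25 for selection).

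| Scenario (effect) | Apparent | Corrected | New patients | Share recovered |
|---|---|---|---|---|
| Death, 8 (0.35) | 0.748 | 0.737 | 0.734 | 0.011/0.014 = 79% |
| Death, 8 (0.20) | 0.663 | 0.646 | 0.641 | 0.017/0.022 = 77% |
| Death, 18 (0.20) | 0.674 | 0.638 | 0.629 | 0.036/0.045 = 80% |
| ECMO at 10%, 9 (0.20) | 0.674 | 0.634 | 0.630 | 0.040/0.044 = 91% |
| Selection from 38 (0.20), repeated in each resample | 0.669 | 0.616 | 0.618 | 0.053/0.051 = 104% |
| Same, selection not repeated | 0.669 | 0.654 | 0.618 | 0.015/0.051 = 29% |

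**8. Sensitivity to the set-up.** In step 3 the linear predictor has SD = effect x √8, that is 1.56, 0.99 and 0.57. A separate simulation with SD 1.5, 1.0 and 0.5 and 100,000 new patients gave optimism of 0.018-0.043 at 18 predictors and 0.027-0.064 at 27. Another run covered both independent predictors and pairwise correlation 0.3. It gave 0.005-0.019 at 8 predictors, 0.020-0.047 at 18 and 0.023-0.057 at 27. The conclusion does not depend on independence at the correlation tried.

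**The case against.** The strongest reply is that this is mainly a risk-factor study. According to the Objective section, the investigators "sought to find out the treatment results and prognosis of fulminant myocarditis requiring vasopressors or mechanical assist devices". No score, threshold or clinical use of a model is planned, and correcting a C-statistic does not change which factors are reported or the validity of a pre-specified odds ratio. With 5 to 8 pre-specified predictors the optimism is only 0.006-0.019. The large figures need 27 predictors, 19 of them noise, with weak real effects. All of this is true and limits the weight of the point. It does not remove it: the SAP itself calls the product a prediction model, proposes to report its performance, and does not commit to a small model.

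Second, the 92-98% pass rate for Hosmer-Lemeshow is close to the test's nominal 95%, as expected when the simulated model has the right form. Rejection rose to 98% for a strong omitted quadratic term, though it was only 5-7% for two milder misspecifications. So the pass rate is not separate evidence of harm. It shows that the test, in development data, does not detect overfitting.

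Third, the ECMO rates are assumptions, and it is unclear whether the performance sentence covers that model. Those figures are illustrative only.

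Fourth, with six institutions over many years, cross-validation or leaving out one institution at a time could also be defended. That is a choice between validation methods; the plan names none.

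**Conclusion.** The concern holds, as an improvement that should be made rather than a threat to the study. Following the SAP as written would report apparent performance only. For the death model the C-statistic would be too high by about 0.01-0.02 with a small pre-specified model, and by about 0.02-0.06 at the 18 to 27 parameters the plan's rule allows. Calibration slopes at that ceiling run from 0.91 down to 0.65, which Hosmer-Lemeshow would not reveal.

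That optimism exists follows from the method. Its size rests on the implied cohort of 900, the assumed effect sizes and an unstated number of predictors. That the checks use the development data is an inference from the single cohort and the absence of any validation step. The Kaplan-Meier, paired t and Cox results are not affected.

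**What to change.** Replace the performance sentence in the SAP with:

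> For each logistic model we will report the apparent and the bootstrap optimism-corrected C-statistic (discrimination) and calibration slope, repeating any variable selection (and any imputation) in every resample, with a calibration plot; Hosmer-Lemeshow will not be relied on alone.

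The instruction to repeat selection matters: without it, the correction recovered only 29% of the optimism in the selection example.

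As a secondary clarification, add one sentence saying that the events-per-variable rule applies to each model's own events: at most 18 to 27 parameters for about 270 deaths, and the ECMO count divided by 10 to 15 for the ECMO model.

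The cost is one replaced and one added sentence, no new data, and modest extra work in R, which the SAP already names. The work grows if values are incomplete and imputed, which is possible because the Method section has the investigators "Review medical records and reanalyze previously performed blood tests". The visible downside is a lower reported C-statistic, by about 0.01-0.06 depending on model size and effects, and about 0.01-0.02 for 5 to 8 pre-specified predictors.
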